6.4 STUDY INTERVENTION/EXPERIMENTAL MANIPULATION ADHERENCE

Patient adherence is not required for participation in the Effectiveness trial. Patient engagement in MOUD is hypothesized as the clinical Mechanism of Action. Patient self-report will be used to determine whether the patient engaged in MOUD, defined as the ratio of the number of days they reported taking the MOUD medication (numerator) to the number of days during the 6-month follow-up period for which it was prescribed (denominator).

7 STUDY INTERVENTION/EXPERIMENTAL MANIPULATION DISCONTINUATION AND PARTICIPANT DISCONTINUATION/WITHDRAWAL

7.1 DISCONTINUATION OF STUDY INTERVENTION/EXPERIMENTAL MANIPULATION

Stopping the Effectiveness Trial – All medications for OUD and MHS are FDA approved, and the BA psychotherapy has been demonstrated to be effective in numerous RCTs. Therefore, we are not specifying any criteria for suspending or stopping the Effectiveness trial (intervention or evaluation). The

DSMB will review reports about enrollment, adverse events, protocol implementation, and data quality at their meetings and could decide to discontinue the Effectiveness trial.

Discontinuing Treatment – The clinic providers can choose to initiate or discontinue any OUD or MHS treatment at any time during the Effectiveness trial. In this case, the patient would remain enrolled in the study for evaluation purposes. Study participants may also refuse or discontinue treatment at any time during the Effectiveness trial and will remain enrolled in the study for evaluation purposes.

Refusing to Participate in the Evaluation – Study participants may refuse to complete the surveys. Survey refusals will remain in the Effectiveness trial and may continue to receive CoCM for OUD and/or MHS (contributing CMTS data).

7.2 PARTICIPANT DISCONTINUATION/WITHDRAWAL FROM THE STUDY

Patient Requests Study Withdrawal – If a study participant writes to the PI stating that they would like to withdraw from the Effectiveness trial, we will stop collecting survey data and we will not use CMTS data for evaluation purposes after that date. Patients withdrawing from the Effectiveness trial may continue to receive CoCM for OUD and/or MHS or decline further treatment.

PI Withdraws Patient from Study – A PI may terminate a enrollee's participation in the Effectiveness trial for the following reasons:

- The PI learned that the study participant did not meet inclusion criteria or did meet exclusion criteria at the time of enrollment.
- Other unanticipated reasons

Patients withdrawn from the study by the PI may continue to receive CoCM for OUD and/or MHS.

7.3 LOST TO FOLLOW-UP

Definition of Lost to Follow-Up – A study participant will be considered to have been lost to follow-up by the survey team if it has been more than 14 days after the baseline survey was scheduled to be completed or more than 30 days after the 3-month or 6-month follow-up survey was scheduled to be completed.

Retention – Study participants will be able to complete the survey on the phone or on the web. Consenting patients will be asked to provide at least four alternative contacts, in addition to their own telephone number and email address, and to agree for us to contact these alternates if we lose touch with the patient. In addition, to mailing reminders about completing the follow-up surveys, we will also request permission from patients to text and/or email them reminders with a link to the web-based survey. We will identify ourselves as representing the primary care clinic but will not disclose any other details about the purpose for trying to reach the participant. Clinics will be alerted if the data collection team loses touch with the patient and asked to flag the registry so the patient can provide updated contact information at their next visit to the clinic. Patients will receive incentives to complete surveys and this remuneration increases with each subsequent survey.

8 STUDY ASSESSMENTS AND PROCEDURES

8.1 ENDPOINT AND OTHER NON-SAFETY ASSESSMENTS

Screening and Eligibility Assessment – To be enrolled/consented in the Effectiveness trial, a patient must have screened positive for OUD and a MHS in the past six months AND currently meet clinical criteria for ≥2 symptoms of OUD on the DSM-5 checklist *AND/OR OUD diagnosis recorded in the electronic medical record AND a patient encounter in the last 6 months OR OUD diagnosis on problem list PCP reviewed in the last 6 months.*

Survey Administration – Surveys will be administered at baseline, and at 3- and 6-month follow-ups.

Construct/Instrument	Baseline	3-Month Follow-Up	6-Month Follow-Up
Demographics	X		
Social Determinants	X		
Homelessness Screening Clinical Reminder	X		
Legal involvement question (Addiction Severity Index – modified)	X		
Insurance	X		
Pain (PEG)	X	X	X
Alcohol Use (AUDIT)	X	X	X
Opiate Use (BAM-R)	X	X	X
Opiate Craving Question (Addiction Severity Index – modified)	X	X	X
Readiness to Change (ICR)	X		
Other Drug Use (BAM- R)	X	X	X
Recent Experience of Overdose	X	X	X
Health Related Quality of Life (Veterans Short Form-12)	X	X	X
Depression (SCL20)	X	X	X
Anxiety (Neuro-QOL Measure - Anxiety, Short Form)	X	X	X
Trauma (PC-PTSD-5 Criteria A screener)	X	X	X
PTSD (PCL-5)	X	X	X
Access to Care (SPIRIT Perceived Access Inventory)	X	X	X
Service Utilization	X	X	X
Medication Use	X	X	X
Side Effects	X	X	X

Care Management Tracking System (CMTS) – After the last study participant has completed the 6-month follow-up, we will extract information from CMTS. CMTS is a web-based registry hosted by the AIMS Center and used by the care managers to track process and outcomes.²⁰ The CMTS contains clinic-level process of care and patient-level clinical outcome data that shows how patients receive care. For the evaluation, CMTS will be used to measure the number of care manager encounters, the number of

care manager encounters with recorded elements of BA, number of psychiatric case reviews, urine test results, medications prescribed for OUD and MHS, as well as results of state prescription drug monitoring checks to obtain an objective measure of MOUD initiation and adherence. For injectable buprenorphine or naltrexone, clinic staff will likewise record the administration of these injections in the CMTS.

8.2 ADVERSE EVENTS AND SERIOUS ADVERSE EVENTS

8.2.1 DEFINITION OF ADVERSE EVENTS

Definition of an Adverse Events: Any untoward or unfavorable medical occurrence in a human subject, including any abnormal sign (for example, abnormal physical exam or lab finding), symptom, or disease temporally associated with the subject's participation in the research, whether or not considered related to the subject's participation in the research.

We will report the following Adverse Events:

01. Non-suicidal self-injury that did not result in Hospitalization or ED Visit
02. Other _____

Adverse Events will be classified as serious or non-serious; expected or unexpected; and as definitely study-related, probably study-related, possibly study-related, or definitely not study-related.

8.2.2 DEFINITION OF SERIOUS ADVERSE EVENTS

Definition of a Serious Adverse Events: Any adverse event temporally associated with the subject's participation in research that is potentially life threatening, results in death, requires hospitalization, results in persistent or significant disability/incapacity, or any other adverse event that, based upon appropriate medical judgment, may jeopardize the medical or surgical intervention to prevent one of the other outcomes listed here.

We will report the following Serious Adverse Events:

01. Suicide attempt
02. Suicide resulting in death
03. Death (not suicide or unsure if suicide)
04. Non-suicidal self-injury that resulted in Hospitalization
05. Non-suicidal self-injury that resulted in ED Visit
06. Non-lethal overdose (that resulted in hospitalization or ED visit)
07. Non-lethal overdose (that did not result in hospitalization or ED visit)
08. Non-lethal Overdose (with no hospitalization or ED visit)
09. Serious Medication Reaction (that resulted in a clinical encounter)
10. Other: _____

Serious Adverse Events will be classified as expected or unexpected; and as definitely study-related, probably study-related, possibly study-related, or definitely not study-related.

8.2.3 CLASSIFICATION OF AN ADVERSE EVENT

8.2.3.1 SEVERITY OF EVENT

Adverse Events will be considered either serious or non-serious based on the definition of Serious Adverse Event Above.

8.2.3.2 RELATIONSHIP TO STUDY INTERVENTION/EXPERIMENTAL MANIPULATION

All Adverse Events and Serious Adverse Events will be classified as:

01 - Definitely study related (100%)

There is clear evidence to suggest a causal relationship, and other possible contributing factors can be ruled out. The clinical event occurs in a plausible time relationship to study procedures administration and cannot be explained by concurrent disease or other drugs or chemicals. The event must be pharmacologically or phenomenologically definitive.

02 - Probably study related (50-99%)

There is evidence to suggest a causal relationship, and the influence of other factors is unlikely. The clinical event occurs within a reasonable time after administration of the study procedures, is unlikely to be attributed to concurrent disease or other drugs or chemicals.

03 - Possibly study related (1-49%)

There is some evidence to suggest a causal relationship (e.g., the event occurred within a reasonable time after administration of study procedures). However, other factors may have contributed to the event (e.g., the participant's clinical condition, other concomitant events). Although an adverse event may rate only as "possibly related" soon after discovery, it can be flagged as requiring more information and later be upgraded to "probably related" or "definitely related", as appropriate.

04 - Definitely not study related (0%)

The event is completely independent of study procedures administration, and/or evidence exists that the event is definitely related to another etiology. There must be an alternative, definitive etiology documented by the clinician.

8.2.3.3 EXPECTEDNESS

There are numerous risks that are anticipated for this population of patient with OUD and comorbid MHS. These risks are both study-related and non-study-related.

Anticipated study-related risks associated with evaluation activities include:

- 01 psychological distress due to survey questions
- 02 potential loss of confidentiality

Study participants in both the intervention and control groups will be more likely to be started on FDA approved medications or have their dosages increased than non-study participants. Therefore, anticipated study-related risks associated with clinical activities include:

- 01 anticipated side-effects
- 02 opioid craving for those initiating MOUD.

Because of the severity and comorbidity of addiction and mental illness in our study population, it also anticipated that study participants will experience the following non-study related Adverse Events and Serious Adverse Events with a high degree of frequency:

- 01 Non-lethal self-harm (Adverse Event)
- 02 Suicide attempt (Serious Adverse Event)
- 03 Death by suicide (Serious Adverse Event)
- 04 Accidental overdose (Serious Adverse Event)
- 05 Emergency department visits and/or hospital admissions (Serious Adverse Event)

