In 2018, the National Institute of Mental Health (NIMH) issued a Request For Applications (RFA-MH-19-525) titled “Helping to End Addiction Long-term (HEAL) Initiative: Effectiveness Trials to Optimize, Implement, Scale, and Sustain the Collaborative Care Model for Individuals with Opioid Use Disorders and Mental Health Conditions”. Four clinical trials were funded, including the Collaborating to Heal Addiction and Mental Health in Primary care (CHAMP) trial described in this manuscript. The objective of the CHAMP trial was to compare the effectiveness of a Collaborative Care Model (CoCM) intervention designed to co-manage both Opioid Use Disorder (OUD) and common co-occurring Mental Health Symptoms (MHS) to a usual care control condition representing CoCM designed to manage co-occurring MHS only.

This statistical analysis plan (SAP) will comprehensively enumerate the primary and secondary outcomes, and mediating variables, and corresponding analyses.

2. Study design

The CHAMP hybrid type 2a effectiveness-implementation trial was a cluster randomized trial in which clinics were randomized to CoCM for OUD and MHS or CoCM for MHS only. Hybrid type 2a trials compare two clinical interventions and pilot test a practical, but not evidence-based, implementation strategy.

Randomization - Initially 24 clinics were stratified according to one of two CoCM fidelity cohorts (specified as low or high) and healthcare organization and then randomized in a 1:1 ratio by our statistician into one of two arms (intervention or control). Stratification served two purposes. First, stratifying on healthcare organization (each has 2 or 4 clinics in the study) should balance the intervention and control groups according to key system level factors that influence quality and outcomes (e.g., electronic health record quality). Second, stratifying on cohort ensures balance with regard to fidelity to the CoCM model which is likely to be correlated with our primary outcomes. In addition, clinics with lower fidelity were designated to have a longer training duration. An additional 18 clinics were recruited later during the study and they all received the short training duration in order to maximize recruitment, and therefore we did not stratify the randomization of the additional 18 clinics by fidelity but did continue to stratify by health care system.

3. Outcomes

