Primary outcome. There are two primary outcomes (see Table 1). Opioid use is one of our primary outcomes and is measured using item 7E from the Brief Addiction Monitor-Revised (BAM-R) which was derived from the Addiction Severity Index35 by CESATE: “7. In the past 30 days, how many days did you use any of the following drugs: E. Opiates (e.g., Heroin, Morphine, Dilaudid, Demerol, Oxycontin, oxy, codeine (Tylenol 2,3,4), Percocet, Vicodin, fentanyl, etc.)?” Our other primary outcome is mental health related quality of life and is being measured using

the Veterans Short Form Health Survey 12 Mental Health Component Summary score (MCS). Both primary outcomes are assessed at the 6-month follow-up survey.

Secondary outcomes. This study includes 24 secondary outcomes, assessed at both the 3-month follow-up and the 6-month follow-up (Table 1). Secondary outcomes include the use of other drugs, depression, anxiety, PTSD, pain, physical health-related quality of life and perceived access to OUD care (see Table 1). Secondary outcomes also include opioid use and mental health related quality of life assessed at the 3-month follow-up survey. Exploratory outcomes are risk factors for premature mortality, including suicidal ideation, discontinuing MOUD, overdose, suicide attempts, emergency department admission, and hospitalization. Risk factors are collected via survey and adverse event reporting.

Construct/Instrument	Instrument(s)	Baseline	3-Month Follow-Up	6-Month Follow-Up
Multiple Primary Outcomes				
Opioid Use	BAM-R ^{1,2}	X	X	X
Mental health related quality of life (MCS)	Veterans Short Form-12 ³	X	X	X
Secondary Outcomes				
Pain	PEG ⁴	X	X	X
Alcohol Use	AUDIT-C ⁵	X	X	X
Cannabis Use	BAM-R ^{1,2}	X	X	X
Other Drug Use	BAM-R ^{1,2}	X	X	X
Depression	SCL-20 ⁶	X	X	X
Anxiety	PROMIS Measure - Anxiety, Short Form ^{7,8}	X	X	X
PTSD	PCL-5 ^{9,10}	X	X	X
Physical health related quality of life (PCS)	Veterans Short Form-12 ³	X	X	X
Access to Care	APAC ¹¹	X	X	X
Exploratory Outcomes				
Risk factors for mortality	WFS ¹ and Adverse Events	X	X	X
Mediator Variable				
MOUD Consistency	WFS ¹	X	X	X

APAC - Assessment of Perceived Access to Care

BAM-R - Brief Addiction Monitor-Revised

ICR - Individual Change Readiness

MOUD – Medications for Opioid Use Disorder

PCL-5 - PTSD Check List

PC-PTSD-5 – Primary Care PTSD Screen for DSM-5

PCS - Physical health related quality of life

PEG - Pain, Enjoyment of Life and General Activity

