Here the outcome measured at time t , for subject i , in clinic c is denoted by Y_{cit} . To account for the cluster-randomization this model includes a random effect for each clinic denoted as u_c . In order to allow a general longitudinal correlation and variance structure we use three subject-specific error terms denoted by u_{cit} for $t=0, 3, 6$ months. We assume a general 3×3 covariance model for these error terms to provide maximal validity to inference regarding change over time. To allow for potential non-linear change over time, we will enter time as a nominal variable by including dummy codes for the 3 and 6 month time points represented by the variables (3 months) and (6 months). Intervention main effects and interaction between intervention and time indicators capture the difference between intervention clinics and control clinics at each wave – with β_1 representing the adjusted mean difference across intervention groups at baseline (adjusting for the design variables) -- with $\beta_1 + \beta_4$ representing the adjusted mean difference across intervention groups at 3 months – and with $\beta_1 + \beta_5$ representing the adjusted mean difference across intervention groups at 6 months. Therefore, the primary contrasts are given by with β_4 as the 3-month intervention effect, and β_5 as the 6-month intervention effect. Note that each intervention effect accounts for the potential imbalance of outcomes across the intervention and control groups at baseline due to the small number of clusters (β_1) and this is removed from the cross-sectional mean contrasts at each follow-up time to define the key intervention effect parameters. *DesignVars* denotes a vector of covariates that includes: 1) low vs high fidelity, which must be controlled because it was a design/stratification variable for some clinics, and 2) additional covariates theoretically related to both the primary outcome and the probability of not completing follow-up surveys which will aid in enhancing validity against missing data and improving precision of estimation. Specifically, we will include: 1) worried about not have stable housing in the next two months, 2) being on parole or probation and/or presently awaiting charges, trial or sentencing, 3) opioid craving, 4) pain, 5) Audit-C, 6) provider trust (APAC item #6), and 7) any use of other drugs (dummy coding for each class of drug). The pre-specified primary effect of interest will be β_5 , which represents the difference in change from baseline between intervention and control clinics at 6 months. Table S2 presents a shell table for the primary outcome and Figure 2 presents a shell plot. Table S3 presents a shell table for the secondary outcomes.

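### Survey-reported side effects and opioid craving, both named as anticipated study-related clinical risks, have no planned between-arm analysis or follow-up table

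*Protocol*

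**What the plan says.** Protocol 8.2.3.3 (Expectedness) explains that participants in both arms are more likely than non-participants to start medication or have a dose raised. It continues: "Therefore, anticipated study-related risks associated with clinical activities include" two entries, "01 anticipated side-effects" and "opioid craving for those initiating MOUD". It lists two further study-related risks, but those belong to the evaluation activities (distress from survey questions and loss of confidentiality).

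The survey table in Protocol 8.1 has a row for "Opiate Craving Question (Addiction Severity Index – modified" and a row for side effects. Both are marked at baseline, 3 months and 6 months, and neither is restricted to one arm.

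The SAP introduction says the plan "will comprehensively enumerate the primary and secondary outcomes, and mediating variables, and corresponding analyses". Its outcome table and the text of section 3 list neither item as a primary, secondary, exploratory or mediator variable. On harm-related outcomes it says: "Exploratory outcomes are risk factors for premature mortality, including suicidal ideation, discontinuing MOUD, overdose, suicide attempts, emergency department admission, and hospitalization". Craving is in the covariate list of section 4.1 ("3) opioid craving, 4) pain, 5) Audit-C, 6) provider trust (APAC item #6") and is a baseline row in Table S1.

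**The concern.** The intervention is designed to start and adjust MOUD alongside psychotropic medication. If the SAP is followed as written, the trial could claim benefit on opioid use or MCS without a planned comparison of the two clinical risks that the protocol itself attributes to taking part. The data for that comparison are already collected.

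The source matters too. Protocol Table 1 puts monitoring of craving and MOUD side effects in the column of additions for the intervention group, and 6.1.1 says intervention care managers, unlike those in the control arm, specifically monitor OUD outcomes. Sites log the adverse events (10.1.6), so detection of these complaints may differ by arm. The survey runs on one schedule for everyone, its administrators are masked to arm and site (6.3), and patients are not told their clinic's arm (10.1.1.2). It is the better source for an arm comparison.

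**Working it through.** The plan states no figure on this point, so the main check traces each item through the documents.

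| Place | Side effects | Opioid craving |
|---|---|---|
| Protocol 8.2.3.3, clinical risks | named | named, for MOUD initiators |
| Protocol 8.1, survey at 0, 3, 6 months | collected | collected |
| Protocol 9.4.2–9.4.3, outcomes | absent | absent |
| SAP section 3, outcome table | absent | absent |
| SAP 4.1, models | absent | covariate only |
| SAP Table S1, baseline | absent | row by arm |
| SAP Tables S2–S4b, follow-up | absent | absent |

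Count: 2 items × 2 follow-ups = 4 possible comparisons, of which 0 are planned.

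**The SAP's count of 24 secondary outcomes.** The outcome table lists 9 secondary constructs. At two visits that is 9 × 2 = 18, and opioid use and MCS at 3 months bring it to 20. The shortfall of 4 happens to equal the number of missing comparisons, but no listed construct or Table S3 row is craving or side effects. Counting the six drug classes of Table S1 separately gives (7 + 6) × 2 + 2 = 28, which does not reconcile either. The count cannot be taken to include these items.

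**Adverse event codes (Protocol 8.2.1–8.2.2).** The only named non-serious code is "Non-suicidal self-injury that did not result in Hospitalization or ED Visit". Among serious events there is a code for a serious medication reaction that led to a clinical encounter. An ordinary side effect or increased craving could enter only under the open code for other events. The SAP has no adverse event table.

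**Precision if the comparison were added.** Inputs from SAP section 6: 254 enrolled, 28 clinics, cluster-size CV 0.97, and 155 patients at 6 months against 191 at baseline in the interim data. Assumptions: that ratio as the follow-up proportion, equal arms, ICC 0.01, and side-effect rates of 10%, 30% and 50%. The documents give no side-effect rate.

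- Per arm: 254 × (155/191) / 2 = 103.
- Design effect: 1 + ((1 + 0.97²) × 254/28 − 1) × 0.01 = 1.17.
- Half-width of the 95% CI: 1.96 × √(1.17 × 2p(1 − p)/103) = 8.8, 13.5 and 14.7 percentage points at p = 0.10, 0.30 and 0.50.

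Using followed rather than enrolled patients for cluster size gives a design effect of 1.13 and 8.7, 13.3 and 14.5 points. With 206 followed and the SAP's two 6-month ICC estimates, 0.00 and 0.03, the half-widths run from 8.2 to 9.7, 12.5 to 14.8 and 13.7 to 16.1 points.

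**The case against.** Several points on the other side stand.

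- **Other reporting routes exist.** The adverse event definition covers any unfavourable symptom and there is an open code. Adverse events go to the DSMB in an annual summary and expected serious events three times a year (8.2.4–8.2.5). Statisticians hold survey data, adverse events and randomization status for DSMB reports (6.3), and results will go to ClinicalTrials.gov (10.1.9). A reader might infer that the trial would not report these harms at all. The documents do not support that. But none of these routes specifies an arm comparison of the survey items.
- **Section 8.2.3.3 does not define endpoints.** It serves to classify events as expected, and its contrast is participants in both arms against non-participants. An intervention-versus-control comparison does not estimate that excess. It remains useful for weighing the intervention's benefit against its burden.
- **The SAP does not contradict itself.** Its claim of completeness covers primary, secondary and mediating variables, not safety. A reader might take the omission as a breach of that claim, but the sentence does not go so far.
- **Craving is named only for MOUD initiators.** In all patients, a fall in craving through treatment could hide a rise among initiators, and initiators are a post-randomisation subset.
- **The side-effects item is known only by its label.** Its wording, scale and denominator are not given. If it is asked only of medication users, a comparison in all patients would partly measure uptake.
- **Arm-specific monitoring is not absolute.** The schedule of activities lists craving and side effects at care manager visits without distinguishing arms, and control care includes management of psychotropic side effects. Unequal detection is a reasonable expectation, not an established fact.

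**Conclusion.** The concern holds in a limited form. Two clinical risks that the protocol calls anticipated and study-related are measured by survey at both follow-ups, and neither document plans a between-arm analysis or follow-up table of them: 0 of 4 comparisons. This rests on reading the documents, not on any assumption. It is a gap in the planned analysis and presentation of harms, not a failure to monitor safety, and it leaves the primary analysis valid.

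The reason to prefer the survey over site-logged events rests on the intervention-arm monitoring described in Protocol Table 1 and 6.1.1. The precision figures, roughly 9 to 15 points, rest on assumed rates, an assumed ICC and an interim follow-up ratio. They show that only fairly large differences could be excluded, so the results should be read as descriptive.

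A related ambiguity needs settling: SAP 4.1 does not say whether the craving covariate is the baseline or a follow-up value. If it were a follow-up value, the primary models would adjust for one of the named risks.

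**What to change.** 1. In SAP section 3 and Table S3, add survey-reported side effects and opioid craving as descriptive safety outcomes at 3 and 6 months. Present them by assigned arm in all enrolled patients, with 95% confidence intervals that account for clinic and no multiplicity adjustment.
2. Use the ordinal or binary logit model already provided in SAP 4.1, as each response scale allows. The craving item has five ordered levels in Table S1, which suits the ordinal model. Drop craving from the covariates in its own model.
3. Add a descriptive row for patients not on MOUD at baseline who report MOUD at follow-up, labelled as a post-randomisation subset.
4. If the side-effects item is asked only of medication users, report it with that denominator, next to medication uptake by arm.
5. State in SAP 4.1 that the craving covariate is the baseline value.
6. If outcomes are already unmasked, label the additions post hoc.

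The cost is SAP wording and a few table rows, with no new data collection. The downside is a few more unadjusted, imprecise comparisons, which may look less favourable to the intervention.
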